5.0 Research Design

Sample Size. We plan to recruit Veterans with stroke and TBI diagnoses and their informal caregivers who are enrolled at the Michael E. DeBakey VAMC in Houston and the Richard L. Roudebush VAMC in Indianapolis. Once Veterans and their caregivers have been identified and screened for eligibility, 330 dyads (222 Veterans with stroke and their informal caregivers and 108 Veterans with TBI informal caregivers) will be randomized to either the ANSWERS-VA intervention or an educational attention control group. Based on our proposed sample size, we will need to enroll an average of 13 dyads per month to reach our goal over 2 years (September of 2014 through October 31, 2017). At these two sites combined, we will screen at least 1408 stroke survivors and at least 694 TBI survivors over the course of our study. Figure 3 below outlines our participant flow diagram for this study.

Figure 3. Projected Participant Flow Diagram v5-19-2014

[figure not shown]

Our sample demographics will represent the Veteran patient population and their caregivers' demographics at the Houston and Indianapolis VAMCs. While we are expecting to recruit a sizable proportion of African American, Hispanic, and women caregivers of Veterans, our sample may be limited in terms of male caregivers and those from other racial groups due to population mix in this region. Specific strategies for the recruitment and retention of both male and female caregivers, as well as those from various ethnic/racial groups, will be used. We will be sure to include written materials that represent multiple ethnic and racial backgrounds as well as depicting both female and male caregivers.

Methods. This is a randomized, controlled trial to evaluate the ANSWERS-VA intervention among Veterans with stroke or TBI and their informal caregivers. Veteran/caregiver dyads in which the Veteran has suffered a stroke (N = 222) or TBI (N = 108), who have received care at the Michael E. DeBakey VAMC (MEDVAMC) in Houston or the Richard L. Roudebush VAMC (RLR VAMC) in Indianapolis, will be randomized to the ANSWERS-VA intervention group or to an educational attention control group. Both the intervention and control procedures involve 8 telephone sessions delivered over 8 weeks, with a booster session at 12 weeks. Data collections will occur at baseline, 8, 12, 24 weeks, and 1 year after baseline.

Data Analysis. Outcomes will be assessed by trained data collectors who are blinded to the treatment. Caregiver task difficulty, optimism, self-efficacy for caregiving and threat appraisal are proposed as mediators for the intervention effect on the primary outcomes of caregiver's quality of life and unhealthy days. We will test the immediate efficacy of the ANSWERS-VA intervention on these mediators and outcomes from baseline to 8 weeks, and long-term, sustained efficacy at (12 and 24 weeks and at 1 year). Veteran and caregiver characteristics (i.e., demographics, co-morbidities, relationship of caregiver to Veteran, and caregiver assessment of the Veteran's impairment) will be controlled by the stratified randomization process and, as necessary, by covariates included in the models. We will assess the exploratory outcomes of effect sizes for the ANSWERS-VA intervention for the Veteran and caregiver on the secondary outcomes of depressive symptoms, social participation, and quality of the dyadic relationship. We will also assess the outcomes of noncaregiving hours and unhealthy days in caregivers to determine the cost effectiveness of this intervention (see Figure 2).

Figure 2. Research Design v5-19-2014

I denotes weekly intervention nurse calls; IB booster at 12 weeks; A denotes weekly attention control nurse calls; AB attention control booster at 12 weeks. *Data collection calls by blinded research assistants.

Study Timeline. The study timeline is planned for four and a half years. We will devote our efforts to start-up, training, and IRB approvals during year 1 and then proceed to recruitment during months 10-36. We complete the 1-year data collection and data analyses on the primary aims in year 4. In the first quarter of year 5, we will complete the follow-up 1-year data analyses to guide our pre-implementation phase of the ANSWERS-VA intervention (see Gantt Chart in Table 6 below).

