2.0 Rationale and Specific Aims

Project Objectives. The objectives of this study are to conduct a randomized controlled trial (RCT) to evaluate (a) the efficacy of the “Acquiring New Skills While Enhancing Remaining Strengths for Veterans (ANSWERS-VA)” dyadic intervention with Veterans who have sustained a stroke and/or traumatic brain injury (TBI) and their informal caregivers, and (b) estimate effect sizes for the ANSWERS-VA intervention. The ANSWERS-VA intervention will be compared with an educational intervention that will serve as an attention control group.

Specific Aim 1: To tailor the implementation of the ANSWERS-VA intervention to dyads (n=10) consisting of Veterans with stroke and/or TBI diagnoses and their informal caregivers and modify the implementation processes for the RCT.

Specific Aim 2: To test the short-term, intermediate, and sustained efficacy of the intervention (baseline, 8, 12, 24 weeks, and 1 year) for improving the caregivers’ quality of life, task difficulty, threat appraisal, self-efficacy for caregiving, and optimism.

Specific Aim 3: To complete a cost effectiveness analysis of the intervention in comparison to the attention control.

Exploratory Aim 1: To estimate the effect sizes for the dyad outcomes of depressive symptoms, social participation, and quality of the dyadic relationship.

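### The plan has two primary outcomes tested at four visits and no rule for deciding whether the intervention worked; Specific Aim 2 leaves out one of the two primaries

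*Combined protocol and SAP*

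**What the plan says.** Section 5.0, Data Analysis, describes the efficacy analysis in a few sentences:

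- **Outcomes.** It refers to the "primary outcomes of caregiver's quality of life and unhealthy days". Task difficulty, optimism, self-efficacy and threat appraisal are mediators. Depressive symptoms, social participation and dyadic relationship quality are secondary or exploratory.
- **Visits.** "We will test the immediate efficacy of the ANSWERS-VA intervention on these mediators and outcomes from baseline to 8 weeks, and long-term, sustained efficacy", with "sustained efficacy at (12 and 24 weeks and at 1 year" completing the list.
- **Model.** The only reference is to adjustment "as necessary, by covariates included in the models".
- **Second use of unhealthy days.** "We will also assess the outcomes of noncaregiving hours and unhealthy days in caregivers to determine the cost effectiveness of this intervention".

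Section 2.0, Specific Aim 2, covers the same visits but gives the outcomes as caregivers' "quality of life, task difficulty, threat appraisal, self-efficacy for caregiving, and optimism". Unhealthy days is not listed, and nothing in the aim is marked primary.

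**The concern.** Suppose quality of life differs significantly at 8 weeks only, and unhealthy days never does. The plan cannot say whether that is a positive trial. The visit, the outcome and the threshold could all be settled after the results are known, and the error rate of the resulting claim would be unknown. A result on unhealthy days alone raises a further difficulty: Section 5.0 makes it primary, while Aim 2, the efficacy aim, does not mention it. This matters because Section 2.0 makes evaluation of efficacy the first objective of the randomized trial, and Section 7.0 gives implementation across VHA as the long-term goal.

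**Working it through.** **Inputs from the document.** Primary outcomes: 2. Post-baseline visits: 4. Primary tests if each outcome is tested at each visit: 2 × 4 = 8. Sample size: 222 + 108 = 330 dyads. The 330 cannot be reproduced further, because no alpha, power, effect size, standard deviation or dropout is given.

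**Assumptions.** Two-sided 0.05 per test, unadjusted; 1:1 allocation (Section 4.0 aims only for similar group sizes), so 330 / 2 = 165 per arm. Correlations between outcomes and between visits are not given, so a range is shown. Correlated cases were simulated as multivariate-normal test statistics (400,000 draws), with one common correlation between outcomes and one between visits.

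**1. No true effect, any one significant result counts.** If independent:

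- eight tests: 1 − 0.95^8 = 33.7%
- two tests: 1 − 0.95^2 = 9.75%

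| Correlation, outcome/visit | Any of 8 tests | Either outcome, one visit |
|---|---|---|
| 0 / 0 | 33.7% | 9.8% |
| 0.3 / 0.5 | 28% | 9.6% |
| 0.5 / 0.6 | 25% | 9.1% |
| 0.7 / 0.7 | 21% | 8.4% |
| 0.7 / 0.8 | 18% | 8.4% |
| 0.7 / 0.9 | 15% | 8.3% |
| 0.9 / 0.9 | 13% | 7.0% |

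One overall repeated-measures test per outcome gives about the same as the right-hand column: 8.3-9.7% for a visit-average test at outcome correlations from 0 to 0.7.

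**2. No true effect, both outcomes must succeed.** At one named visit: 0.3% (independent) to about 3% (outcome correlation 0.9). If the visit is left open:

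| Correlation, outcome/visit | Both at the same visit | Each at any visit |
|---|---|---|
| 0 / 0 | 1.0% | 3.4% |
| 0.7 / 0.7 | 4.8% | 5.2% |
| 0.7 / 0.5 | 5.7% | 6.4% |
| 0.8 / 0.5 | 7.4% | 7.8% |
| 0.9 / 0.5 | 9.7% | 9.9% |

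**3. Both must succeed, but only quality of life truly responds.** The effect is set at 0.309 SD at every visit, the size that gives 80% power with 165 per arm. A false claim on both outcomes then occurs in 15.1% (same visit) or 18.6% (any visit) at correlations 0/0. This falls to 5.7% or 6.6% at 0.7/0.9 and to about 5% at still higher correlations. At one named visit it is 2.5-4.0%, and it cannot exceed 5% for an effect of any size.

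**The case against.** Four points can be made for the plan.

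- **It does rank outcomes.** Section 5.0 separates primaries, mediators and secondary outcomes. This stands: the lack of ranking is confined to Aim 2, and the mediators do not belong in the count of primary tests.
- **Immediate and sustained efficacy may be separate questions, each with its own claim.** If so, pooling eight tests into one family is a reviewer's choice. But neither question is called primary, and three visits share the sustained label. The timeline, with primary-aim analyses in year 4 and follow-up 1-year analyses in year 5, is the nearest thing to a hierarchy, and it names no deciding visit.
- **A repeated-measures model, or a both-outcomes rule, may be intended.** Neither is stated. The first leaves about 7-10% if either outcome suffices. The second controls the error at one visit but not reliably over four.
- **Figure 2 and the appendices are not shown.** They may label outcome roles. The appendix titles list study materials and instruments, and none points to an analysis plan.

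A reader might infer three stronger things that the documents do not support. One is that the trial has a 34% false-positive rate: that figure needs eight independent tests, and repeated measures on the same caregivers are likely to be correlated. Another is that Aim 2 excludes unhealthy days as efficacy evidence: it only fails to list it, and since the instruments are not supplied, its overlap with quality of life cannot be checked. The third is that using unhealthy days for both efficacy and cost is a contradiction: one variable can serve both, if the plan says so.

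**Conclusion.** The omission is clear from the text: two primary outcomes, four visits, and no deciding visit or overall test, one-or-both rule, alpha or error control. The mismatch with Aim 2 is limited to one unlisted variable and the absence of ranking. This must be fixed, because a deciding visit cannot be chosen fairly once the results are known.

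The size of the risk is undetermined, because it depends on the rules that are missing. At an assumed 0.05:

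- **Any one result counts, no true effect:** about 13-34% over eight tests, with 34% the independent-test ceiling; about 7-10% over two tests.
- **Both required, one named visit:** at or below 5%.
- **Both required, four visits:** about 1-10% with no effect, and about 5-19% for a false claim on both if only quality of life responds.

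Confidence in the omission is high. The percentages are illustrations that rest on assumed correlations and an assumed alpha.

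**What to change.** Before unblinded data are seen:

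1. **Align Aim 2 with Section 5.0.** List both primaries in each place, with the four mediators as secondary or mechanistic. State that unhealthy days has both an efficacy and a cost role, if that is intended.
2. **Prespecify the test.** For each primary outcome choose either one primary time point or one overall repeated-measures treatment test, and name the model. The choice is the sponsor's.
3. **State the success rule.** If either outcome suffices, use Holm across the two at an overall two-sided 0.05. If both must succeed, test each at 0.05.
4. **Demote the remaining visits.** Report them as secondary with estimates and confidence intervals, or test them in a fixed order that continues only if both outcomes succeeded at the previous step.

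No new data are needed. The cost is some power, which can only be illustrated because the documents give no effect size, power or dropout. With 165 per arm and an effect of 0.309 SD, set to give 80% power at 0.05, power for one outcome at the first Holm step (0.025) is 71%. With an assumed 20% dropout (132 per arm) the fall is from 71% to 60%. If both outcomes must succeed and both respond equally, power for the pair is about 64-72% at outcome correlations from 0 to 0.7.

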6.0 Data Management

Database. The REDCap (Research Electronic Data Capture) database system will be implemented to collect data for this study. Study data kept on the REDCap database will not contain any PHI or PII. The project manager, data collectors and/or intervention specialists at Indianapolis and Houston will enter survey data and intervention data in this database. REDCap is a software toolset referred for electronic collection and management of research data. REDCap provides a secure, web-based environment with an intuitive interface for users to enter data and have real time validation rules at the time of entry. The system offers easy data manipulation with logged auditing, functionality for reporting, monitoring and querying patient records, and an automated export mechanism to common statistical packages such as: SPSS,

SAS, Stata, R/S-Plus. Data will be entered into REDCap by the project manager, data collectors and/or intervention specialists in Indianapolis and in Houston.

Data Storage & Security. The servers hosting REDCap are physically located in a secured and environmentally structured computer operations center on the Indiana University (IU) Bloomington campus and are supported by University Information Technology Services (UITS) server and database administrators. To comply with HIPAA guidelines, processes and procedures have been documented and implemented to ensure the security and protection of the study data within the computer operations center, the servers, and the database. There are two secure means of access to the study data for study members who are granted access: 1) via the application by use of IU's Central Authentication Service (CAS) and project database specific permissions; and, 2) via direct access to the database by use of secure database authentication. In each case, the PI will identify who has relevant access to the study data and what permissions each individual shall have. REDCap utilizes SSL (https) encryption for secure connectivity.

We will keep a paper enrollment form that will contain the following PHI/PII: name, MRN, address, and contact information. The enrollment form will be stored in a locked file cabinet in a locked office utilized for the study at the Indianapolis VAMC for patients/caregivers enrolled from the RLRVAMC and at the Houston VAMC for patients/caregivers enrolled at the MEDVAMC. The information from this enrollment form will be added to an electronic crosswalk that ties this information to the study ID that will be established at the coordinating center at the RLR VAMC in Indianapolis in an access-controlled project folder on the secure VA network research drive which is behind the VA firewall. Access to this folder will be given to the study personnel in Houston so that the information can be shared in a secure manner. PHI/PII will not be stored on any other paper research records or in the electronic database (REDCap).

Audio recordings of the calls administered by the intervention specialists will be stored at the Richard L. Roudebush VAMC in the access-controlled project folder on the secure VA network Q. According to the VA's OIS Risk Based Decisions (RBD)Memorandum, recordings will be made with devices that are not technically capable of FIPS 140-2 compliant encryption and at this time there is no cost effective alternative solution that exist. This RBD is permanent or until such a time that a FIPS 140-2 compliant audio recording device is available. Recordings will be uploaded to the VA project folder for backup, and then permanently deleted from the devices.

Missing Data. We will incorporate several strategies to minimize missing data. For example: (a) a tracking database will be incorporated to insure timely follow-up contacts and maintain current contact information; (b) calls with dyads will be scheduled ahead of time and at a time which is convenient for the Veteran and caregiver; (c) essential data fields will force data collectors to provide an appropriate value (including use of special missing codes describing reason data are missing), rather than leave blank; (d) data will be entered into a secure system backed up nightly by the university; (e) paper forms will be available for data collection when direct entry is not possible; and (f) data will be inspected quarterly during data collection for errors and missing values.

Data Transfers. In order to receive the subject lists from Houston, the data collector there will run the list using a template built by a Clinical Applications Coordinator (CAC) from Indianapolis. Then the data collector at Houston will be given access to the Indianapolis study folder on the

secure VA Q-drive and the REDCap database in order to store data collected from that site. Paper data collection forms, including the enrollment form and copies of the Informed Consents and HIPAA Authorizations will be sent to the coordinating center in Indianapolis on a quarterly basis using a trackable courier service.

Data Sharing. We will also make the database available to others when we are finished reporting our primary results. Special measures will be taken to ensure that caregivers and Veterans are not identifiable by any data that are shared. Close collaboration with [name] and her research team will be necessary for the use of shared data.

7.0 Risks & Benefits

Risks. The main risks to subjects are loss of confidentiality and discomfort in answering certain questions. Specific steps to minimize these risks are detailed in section 9.0. Should any loss of confidentiality be identified, the study PI will, within 24 hours of the identification of this breach, contact the ACOS for Research, the IRB and R&D committees, and the Information Security Officer (ISO) and Privacy Officer (PO) at the coordinating site as well as the site PI at Houston should the loss of confidentiality occur there.

Benefits to Participants. Our hope is that the ANSWERS-VA intervention will provide Veterans with brain injury and their loved ones with a core set of practical skills that each can use in coping with and managing the symptoms of brain injury. Participants in the intervention group will receive 9 calls from a trained intervention specialist who will work with the dyad on education and counseling-based skills training and cognitive and physical rehabilitation techniques. They will also receive the ANSWERS-VA binder (see Appendix 12 in section 11.0) which contains written educational materials, skills training, worksheets, and additional resources. The control group will also receive the ANSWERS-VA binder, but not until they complete the final data collection interview for the study.

Benefits to Society. The long term goal of this study is to implement this intervention for Veterans with stroke and TBI and their family caregivers across VHA by offering comprehensive training and support. Therefore, this program may also benefit the health-related quality of life of future Veterans with stroke/TBI and their caregivers. The ANSWERS-VA intervention will also foster translation into practice due to eliminating costly in-patient and in-home visits.

8.0 Data Safety and Monitoring

Any ongoing data safety and monitoring issues will be presented to the larger investigators group. This group of investigators is comprised of VA and non-VA representatives with a diverse background in nursing, medicine, traumatic brain injury, biostatistics, stroke and caregiving. This group will monitor recruitment, enrollment, data collection, intervention procedures, and participant safety issues such as adverse events and protocol deviations on an ad hoc basis. This is a minimal risk study, and we do not anticipate any study-related, serious adverse events. However, we will track all adverse events and will report any serious adverse events to the IRB as a reportable VA event per VA policy.. At continuing review, the IRB will receive a copy of all Adverse Events not requiring prompt reporting.

9.0 Privacy/Confidentiality Issues

The only identifiable information this study plans to collect are the subjects' names, addresses, telephone numbers, social security number, hospital discharge date, date of diagnosis, and voice recordings of the intervention and control calls, and all of the PII being collected will be stored at the RLRVAMC and MED VAMC. To add further protections, subjects will be assigned a unique study identification (ID) number. This number will be used as the identifier for the study data that will be stored in the REDCap database and for the audio recordings. The study ID will also connect the Veteran and caregiver data that is abstracted through CPRS chart reviews. The crosswalk file that links the subject ID number with the Veterans and caregivers will be kept at the VA on a network server in a secure file behind the VA firewall and will only be accessible to authorized study personnel. All study forms which contain PHI/PII will be locked and secured in file cabinets only accessible to authorized study personnel. When study personnel are no longer part of the research team, the PI will remove all access to study data from this individual, and the R&D office will be notified so that VA network access can be terminated.

Subjects will be instructed that they may refuse to answer any question with which they are uncomfortable, and they will be assured that they may withdraw from the study at any time without repercussions of their healthcare and the healthcare of the Veteran with whom they have a relationship.

10.0 Follow-up and Record Retention

This study received an award acceptance letter from VA HSR&D in October of 2012. It received funds at the beginning of fiscal year 2014 which was October 1, 2013, and it is anticipated that the study will be completed on March 31, 2018.

All data collected will be stored indefinitely or until the VA Records Control Schedule signifies the destruction timeframe of VA research records. At the time of data discard, all paper will be shredded, and PC hard drives and network files will be sanitized.

After the study is closed, and all analysis and papers are complete, all data that is stored at IU will be returned to the VA.

